1.0 Clinical Investigation Plan Overview

This preliminary, prospective, single-arm clinical study will evaluate the safety and potential efficacy of Autologous Muscle Derived Cells for Urinary Sphincter Repair (AMDC-USR) for the treatment of male stress urinary incontinence (SUI) that develops following prostate surgery.

Prostate surgery can induce iatrogenic sphincter damage resulting in long-term SUI. Therefore, augmenting sphincter function may be beneficial to patients. Autologous muscle cell therapy, which involves isolation of cells from skeletal muscle biopsies, ex vivo expansion, and subsequent injection into the urethral sphincter, may serve as a potential durable therapy. In animal studies, muscle derived cells have successfully integrated within tissue to improve sphincter function. Intrasphincteric injection of AMDC-USR is expected to produce localized tissue changes near the injection site and is not expected to produce a systemic effect.

Patients will receive intrasphincteric injection of a single treatment of 150×10^6 AMDC-USR. For entrance into the study, patients must meet the study inclusion criteria and must not meet any of the exclusion criteria. Patients will have quantitative and qualitative measures of incontinence assessed before treatment and at various times after treatment.

The study will treat up to 30 patients at up to 5 clinical sites. Enrollment is expected to be completed within 2.5 years of initiating the study. Patients will be followed for 24 months post-treatment. The first 3 patients at each site must reach 1-month follow-up before subsequent patients can be treated at that site.

Male patients at least 18 years of age who have undergone prostate surgery at least 12 months prior to screening and who present with symptoms of SUI will be screened for eligibility for study participation. To participate, patients must meet all inclusion criteria and none of the exclusion criteria. Eligible patients will have muscle tissue harvested using a needle biopsy technique during an outpatient procedure. The harvested muscle tissue will be placed in a hypothermic medium and transported to the manufacturer for cell processing in their laboratory in Pittsburgh, PA (USA). The muscle derived cells (MDC) will be isolated and expanded in culture over several weeks to a final dose of $150 \times 10^6 \pm 20\%$ AMDC-USR.

Due to the personalized nature of each autologous product, some products may not meet all

release specifications of purity and dose. If a product meets all predefined safety criteria, the product may be offered to the patient at the physician's discretion. Affected patients will be notified prior to their injection procedure and must provide consent of their willingness to receive an injection of product that does not meet all target criteria.

After reaching the desired concentration, the isolated and expanded AMDC-USR will be frozen and shipped back to the investigating physician. The physician will thaw the AMDC-USR and dilute the sample with an approximately equal volume of physiological saline. Under direct vision, the resulting suspension will be injected into the patient's urethral sphincter in a brief outpatient procedure.

Patients will be assessed for safety and improvement in urinary incontinence symptoms at 1, 3, 6 and 12 months following treatment. Adverse events will be assessed at all follow-up visits, as well as during follow-up calls at 1-2 days, 1 week, and 24 months. A study overview is depicted in Figure 1.1.

The primary safety measures will be the incidence of study product-related serious adverse events (SAEs) and the incidence of study product-related, biopsy procedure-related, and injection procedure-related adverse events and post-void residual (PVR) urine volume. Secondly, potential efficacy will be evaluated based on reduction in the amount of urine leakage, as assessed by a 24-hour pad test at 1, 3, 6, and 12 months following treatment. Changes in patient-reported incontinence symptom severity, quality of life (QOL), and erectile dysfunction (ED) symptoms will also be assessed at 1, 3, 6, and 12 months following treatment.

[figure not shown]

Figure 1.1. Study flow diagram

2.0 Objectives of the Clinical Study

2.1 Primary Objectives

The primary objective of this study is to evaluate the safety of AMDC-USR during the

24 months following treatment of SUI in male patients who have undergone prior prostate surgery.

Safety will be determined by the frequency and severity of adverse events related to study procedures and study product through 24 months following treatment of SUI in male patients who have undergone prior prostate surgery. PVR volume will be assessed through 12 months post-treatment to monitor potential retention or obstruction.

2.2 Secondary Objectives

In addition to the primary objective listed above, the following secondary objectives will be evaluated in this clinical study:

- Efficacy of AMDC-USR in the reduction of SUI symptoms at 1, 3, 6, and 12 months post-treatment
- Effect of AMDC-USR on QOL at 1, 3, 6, and 12 months post-treatment

Additionally, information on ED symptoms will be collected at 1, 3, 6, and 12 months post-treatment.

3.0 Product Description and Intended Use

3.1 General Product Description

Please reference the Investigator's Brochure for a detailed description of the product and dose to be used in the clinical study.

[REDACTED]

Cook MyoSite, Incorporated will perform cell processing and preparation of cell suspensions for study use in their cell processing facility in Pittsburgh, Pennsylvania (USA). Cell processing will begin with isolation of cells from the patient's tissue. The cells will then be grown in culture and

expanded in number. The culture process produces a final cell culture that is enriched in myogenic cell content. Cell culture will be performed in medium consisting of physiological saline solution with cell nutrients. Cell processing will follow current Good Manufacturing Practice (cGMP) methodologies to prevent contamination and to preserve tissue function and integrity. These practices will include defined procedures for tissue and cell handling, processing, and identification.

Each AMDC-USR study agent vial supplied to the clinical site will contain cryogenically preserved autologous muscle derived cells, prepared to $\pm 20\%$ of the stated total viable cellular dose at the time of packaging, [REDACTED]

[REDACTED] Each study agent vial will be thawed at the clinical site prior to use and diluted with an approximately equal volume (2 mL) of injectable sodium chloride (saline) at physiological concentration, [REDACTED]

Materials contacting the patient's urethral tissue will include the patient's own muscle derived cells, the cryogenic medium in which the cells are suspended and shipped, and the physiological saline used to dilute the mixture for injection.

3.1.1 Dose Justification

A dose of 150×10^6 AMDC-USR was chosen [REDACTED]

[REDACTED]

Systemic adverse effects attributable to AMDC-USR have not been observed following intrasphincteric injection of AMDC in non-clinical¹ and clinical²⁻⁴ studies. Therefore, delivery into the urethral sphincter of men is unlikely to produce systemic responses.

Because the risk to patients from adverse effects from the cells is expected to be the same as in other studies for sphincter-related indications, a dose with potential beneficial effect will be evaluated in the initial study.

3.2 Indication for Use

The AMDC-USR treatment is indicated for reduction in symptoms of urinary incontinence and improvement in patient QOL in men with stress urinary incontinence.

3.3 Product Identification and Tracking

Products under investigation will be tracked by the clinical site throughout the course of the study through the use of a product log, which includes information such as lot numbers, quantity, and disposition of products. Additionally, information such as the quantity and lot number(s) of products used in patients will be recorded on Case Report Forms (CRFs).

Each product is manufactured individually and labeled with a unique product code for identification and traceability. All cell preparations will be transported in identical vials with the same volume of transport medium and reconstituted to the same final volume prior to injection. Vials will be identified by a product code containing lot number, patient initials, and six unique digits. Additional procedures have also been established to ensure traceability.

3.4 Instructions for Use

The study procedure guidelines, which will be provided to physicians and appropriate study staff at the time of training, must be followed for step-by-step instructions for performing the following:

¹ Please reference the Investigator's Brochure, Section 5.3, Toxicology.

- Obtaining the muscle biopsy
- Packaging and shipping the muscle biopsy
- Complete instructions including storage and handling requirements
- Resuspending the final product (AMDC-USR)

Muscle Biopsy

The biopsy procedure will involve minor surgery to collect approximately 50-250 mg of the vastus lateralis muscle using a sampling needle. Prior to the biopsy, patients who are currently taking any form of anticoagulant medication must stop using the medication as per standard of care for outpatient surgery procedures. Antianxiety medication, analgesia, or minimal sedation may be provided according to each site's standard of care. [REDACTED]

Several passes of the biopsy needle may be required to obtain a satisfactory sample of muscle tissue. Additionally, if the first biopsy does not produce an adequate sample for product isolation, it may be necessary for the patient to return for another biopsy procedure. The maximum permissible number of biopsy needle passes and the total number of biopsies is contingent upon patient tolerance and the satisfactory procurement of muscle tissue.

Using aseptic technique, the biopsy tissue will be transferred to the Biopsy Medium Vial. The Biopsy Medium Vial will be closed and packaged according to the study procedure guidelines for shipment to Cook MyoSite, Incorporated.

Dilution and Preparation for Injection

The frozen product will be thawed for at least 8-10 minutes at room temperature. The 2 mL of cell suspension will be diluted with 2 mL of physiological saline for an approximate total volume of 4 mL. The entire vial contents will be used for injection.

Cell Injection

The study agent (AMDC-USR) will be injected into the urethral sphincter. A course of prophylactic antibiotics will be given prior to the injection procedure. Ultrasound may be performed to aid in the injection procedure. Under direct vision, multiple injections will be

performed to circumferentially distribute AMDC-USR within the striated muscle of the urethral sphincter. Materials contacting the urethral tissue will include the patient's own AMDC-USR, the cryogenic medium in which the AMDC-USR are suspended and shipped, and the physiological saline used to dilute the mixture for injection. Prior to the injection, patients who are currently taking any form of anticoagulant medication must stop using the medication as per standard of care for outpatient surgery procedures. Antianxiety medication, analgesia, or minimal sedation may be provided according to each site's standard of care or physician's discretion.

After the injection is completed, the injected area will be examined for any excessive bleeding or excessive trauma. The patient will be asked to void, and an ultrasound/bladder scan will be performed to determine PVR urine volume.

4.0 Summary of Preliminary Studies

Please reference the Investigator's Brochure for a summary of non-clinical testing and a summary of previous clinical experiences with this product or similar products.

5.0 Risk Analysis and Risk Assessment

5.1 Risks and Foreseeable Adverse Events and Adverse Product Effects

Please reference the Investigator's Brochure for a list of specific risks of study procedures and study products.

5.2 Methods to Minimize Risks

Only trained healthcare professionals who are experienced with cystoscopy and urethral injection will administer this product. Patients will be selected according to the indication and in accordance with inclusion/exclusion criteria outlined in this document. Adherence to and training on the research clinical investigation plan (CIP) are necessary to reduce material- and procedure-related risks. Routine catheterization and venipuncture will be performed by qualified personnel.

The product design, non-clinical testing, clinical study design, and study procedure guidelines are intended to minimize the risks associated with the use of this product. The risks of the study have been minimized and the potential benefits outweigh the risks.

6.0 Design of the Clinical Study

6.1 Design of Study

This preliminary, prospective, single-arm clinical study will evaluate the safety and potential efficacy of AMDC-USR for the treatment of male SUI that develops following prostate surgery.

The study will treat up to 30 patients (treated with 150×10^6 AMDC-USR) at up to 5 clinical sites. Enrollment is expected to be completed within 2.5 years of initiating the study. Patients will be followed for 24 months post-treatment. The first 3 patients at each site must reach 1-month follow-up before subsequent patients can be treated at that site.

6.2 Inclusion and Exclusion Criteria

Patient eligibility for enrollment shall be based on known information at the time of the screening. Information obtained at a later date may contradict these criteria, but this will not be considered a deviation to the CIP.

Inclusion Criteria

A patient is deemed suitable for inclusion in the study if the patient meets the following criteria:

1. Male, at least 18 years old, with primary symptoms of SUI following prostate surgery that occurred at least 12 months prior to enrollment, as confirmed by medical history and clinical symptoms, including a focused incontinence evaluation.
2. Patient has undergone prostate surgery, such as radical prostatectomy or prostate resection, but has not undergone radiation therapy, cryotherapy, or high-intensity focused ultrasound of the prostate.
3. SUI severity must be ≥ 10 g and < 400 g of urine leakage over 24 hours, as determined by a 24-hour pad test during screening.²

² Moore, et al.⁵ suggest > 4 g as a minimum pad weight gain for incontinence in men, but that the upper limit for normal pad weight gain should be 8 g. Thus, > 8 g would be considered incontinence in men. Kumar, et al.⁶ suggest > 400 g/24 h is high-grade incontinence (or total incontinence), and recommend men in this category receive an artificial urinary sphincter.

4. Patient has failed to achieve acceptable resolution of SUI symptoms following prior therapy.

Exclusion Criteria

A patient is excluded from enrollment into the study if any of the following are true:

Patient History-based Criteria:

1. Simultaneously participating in another investigational drug or device study or has completed the follow-up phase for the primary endpoint of any previous study less than 30 days prior to the first evaluation in this study.
2. Previously treated with an investigational device, drug, or procedure for urinary incontinence within 6 months prior to signing consent.
3. Has ever been treated with a cell therapy for urinary tract dysfunction.
4. Has an artificial sphincter.
5. Previously treated with a periurethral balloon or adjustable sling for urinary incontinence.
6. Symptoms of stress urinary incontinence prior to prostate surgery.
7. Symptoms of only urge urinary incontinence as noted by basic evaluation of etiology from patient medical history, including a focused incontinence history.
8. Symptoms of overflow incontinence as noted by basic evaluation of etiology from patient medical history, including a focused incontinence history.
9. Symptoms of urinary incontinence in which stress urinary incontinence is not the predominant factor.
10. Routinely has more than 2 episodes of awakening to void during normal sleeping hours.
11. Urinary incontinence of neurogenic etiology or uncorrected congenital abnormality leading to urinary incontinence.
12. Indwelling urinary catheter or requires intermittent catheterization for bladder emptying.
13. Neuromuscular disorder (e.g., Parkinson's disease, muscular dystrophy, multiple sclerosis) that could lead to urinary incontinence.
14. Morbidly obese (BMI \geq 35).
15. Uncontrolled diabetes.
16. Adult nocturnal enuresis.
17. Severe, chronic constipation.

18. Compromised immune system due to disease state, chronic corticosteroid use, or other immunosuppressive therapy.
19. History of pelvic organ radiation (e.g., brachytherapy, transurethral microwave therapy [TUMT], transurethral radiofrequency needle ablation [TUNA]).
20. History of high-intensity focused ultrasound (HIFU) treatment of the prostate.
21. History of cryotherapy treatment of the prostate.
22. Medical condition or disorder that may limit life expectancy or that may cause CIP deviations (e.g., unable to perform self-evaluations or accurately report medical history, urinary symptoms, or data).
23. History of bleeding diathesis or uncorrectable coagulopathy.
24. Known allergy or hypersensitivity to bovine proteins or allergens, gentamicin sulfate, or ampicillin that medically warrants exclusion as determined by the physician.
25. Unstable prostate-specific antigen (PSA) for 12 months as determined by the physician.
26. Any non-skin cancer that has necessitated treatment within the past 12 months.
27. Known history of abnormal detrusor activity.
28. Known history of adult vesicoureteral reflux.

Patient Physical Examination or Testing-based Criteria:

1. Does not have a viable mucosal lining along the urinary tract.
2. Current or history of fistula involving the urethra, bladder, or rectum.
3. Urethral stricture or bladder neck contracture requiring intervention to reopen (planned intervention or history of intervention)
4. Current or history of bladder stones.
5. Failure to produce a leak during the bladder stress test.
6. Moderate or severe urethral fibrosis at likely injection site.
7. Voiding difficulty (complains of difficulty emptying the bladder following ultrasound/bladder scan).
8. PVR urine volume ≥ 100 mL,⁷ determined by ultrasound/bladder scan, after repeated testing (i.e., the patient was asked to revoid and the PVR volume was still ≥ 100 mL).
9. Tests positive for Hepatitis B (required tests: Hepatitis B Surface Antigen [HBsAg] and Anti-Hepatitis B Core Antibody [Anti-HBc]), Hepatitis C (required test: Hepatitis C Antibody [Anti-HCV]), HIV (required tests: HIV Type 1 and 2 Antibodies [Anti-HIV-1, 2]), and/or Syphilis.

Patient's Current Status-based Criteria:

1. If previously treated for prostate cancer, evidence of recurrent prostate cancer as determined by the physician during screening.
2. Does not use external collection device for SUI symptoms (e.g., pads, condom catheter, etc).
3. Cannot be, or is not willing to be, maintained on a stable dose or frequency of medication known to affect lower urinary tract function, including but not limited to, anticholinergics, beta 3 adrenergic receptor agonists, tricyclic antidepressants, SNRI or SSRI antidepressants, diuretics, or alpha-adrenergic blockers, or phosphodiesterase type-5 inhibitors, for at least 2 weeks prior to screening; or use of these medications is likely to change during the 12 months following treatment.
4. Cannot, or is not willing to, maintain the current treatment regimen for existing conservative therapy (e.g., pelvic floor muscle training routine, incontinence medications), excluding penile clamps.
5. Cannot, or is not willing to, stop use of penile clamp during the course of the study.
6. Requires prophylactic antibiotics for chronic urinary tract infections, cystitis, urethritis, prostatitis, orchitis, epididymitis, or balanitis, or has required 2 or more courses of antibiotics for lower urinary tract infections in the 2 months prior to signing consent.
7. Any condition, including current infection, which could lead to significant postoperative complications.
8. Current or acute conditions involving cystitis, urethritis, prostatitis, balanitis, orchitis, or epididymitis.
9. Refuses to provide written informed consent.
10. Not at least 18 years of age.
11. Not available for, or willing to comply, with the baseline and follow-up evaluations as required by the CIP.

6.3 Endpoints

6.3.1 Primary Endpoints

The primary safety endpoints include:

- Study product-related SAEs reported through 24-month follow-up;

- Study product-related, biopsy procedure-related, and injection procedure-related adverse events reported through 24-month follow-up; and
- PVR urine volume reported through 12-month follow-up.

6.3.2 Secondary Endpoints

The secondary endpoints include:

- Reduction in amount of urine leakage, as assessed by 24-hour pad test at 1, 3, 6 and 12 months post-treatment;
- Change in patient-reported incontinence symptom severity, as assessed by questionnaires at 1, 3, 6 and 12 months post-treatment; and
- Change in patient-reported QOL, as assessed by questionnaires at 1, 3, 6 and 12 months post-treatment.

Changes in ED symptoms will also be assessed at 1, 3, 6 and 12 months post-treatment.

6.3.3 Rationale for Endpoints

This is a preliminary study to assess the safety of intrasphincteric injection of AMDC-USR in male patients. Safety assessment will be based on the occurrence of product- and study procedure-related adverse events. Additionally, PVR volume will be assessed throughout the study to monitor potential retention or obstruction.

Efficacy measurements will be used in this study to assess the severity level of an individual's incontinence symptoms and the extent to which incontinence symptoms impair quality of life. Measures to assess incontinence include a 24-hour pad test, the International Consultation on Incontinence Questionnaire (ICIQ),^{8,9} the Incontinence Quality of Life (IQOL) questionnaire,^{9,10} the Patient Global Impression of Severity (PGI-S),^{11,12} the Patient Global Impression of Improvement (PGI-I),^{11,12} and the International Prostate Symptom Score (I-PSS).^{13,14}

Since SUI and ED can be comorbidities that develop following prostate surgery, the 5-Item International Index of Erectile Function (IIEF-5)¹⁵ questionnaire will be used to monitor symptoms of ED.

6.4 Variables to be Measured to Demonstrate Achievement of Endpoints

Safety endpoints will be measured as follows:

- Study product-related SAEs reported through 24-month follow-up;
- Study product-related, biopsy procedure-related, and injection procedure-related adverse events reported through 24-month follow-up; and
- Ultrasound/bladder scan determination of PVR volume on the day of injection and at 1, 3, 6 and 12 months post-treatment.

The secondary efficacy endpoints will be measured as follows:

- Reduction in amount of urine leakage from baseline as assessed by 24-hour pad test at 1, 3, 6 and 12 months;
- Change from baseline in patient-reported outcomes for incontinence symptom severity and QOL will be measured by ICIQ, IQOL score and subscores, I-PSS, and PGI-S score at 1, 3, 6 and 12 months; and
- Change in patient-reported incontinence symptom severity will also be measured by PGI-I score at 1, 3, 6 and 12 months.

In addition, change from baseline in patient symptoms of ED will be measured by the IIEF-5 questionnaire at 1, 3, 6 and 12 months. Patient clinical information including details of prior procedures for prostate surgery, underlying reason for prostate surgery, underlying disease severity, and any procedures or revisions following the incident procedure to address disease or SUI symptoms will be collected and evaluated as appropriate.

The clinical data will be collected on standardized Case Report Forms (CRFs). The schedule for assessments is summarized in Table 6.1.

Table 6.1. Data collection schedule

	Screening	Biopsy	Post-biopsy	Treatment	Post-treatment						
	Visit 1	Visit 2	Phone	Visit 3	Phone	Phone	Visit 4	Visit 5	Visit 6	Visit 7	Phone
	Week 1-8 ^a	Week 2-10	Week 3-11	Day 0	Day 1-2	Week 1	Month 1	Month 3	Month 6	Month 12	Month 24
Event	Screening	Biopsy	Follow-up	Injection	Follow-up	Follow-up	Office Visit	Office Visit	Office Visit	Office Visit	Follow-up
Informed Consent	X										
Inclusion/Exclusion ^b	X										
Medical History	X										
Clinical Assessment	X						X	X	X	X	
Physical Examination	X										
Vital Signs	X										
Medication Log	X	X	X	X	X	X	X	X	X	X	X
Urinalysis	X			X			X	X	X	X	
Urine Culture ^c				X							
Bladder Stress Test	X									X	
24-hour Pad Test	X			X			X	X	X	X	
Post-void Residual Volume	X			X			X	X	X	X	
Questionnaires ^d : ICIQ, IQOL, PGI-S, I-PSS, IIEF-5	X			X			X	X	X	X	
Questionnaire ^d : PGI-I							X	X	X	X	
Blood Samples	X ^f						X			X	
Cystoscopy	X ^e			X						X	
Muscle Biopsy		X									
Injection				X							
Adverse Events	X	X	X	X	X	X	X	X	X	X	X
Telephone Follow-up			X		X	X					X

^a It is recommended that screening tests conducted in Visit 1 be completed within 8 weeks preceding the biopsy visit.

^b An electronic case report form system tracks inclusion/exclusion screening information.

^c This test must be completed if the urinalysis is positive for nitrites or leukocyte esterase on the day of scheduled injection. Urine culture may also be performed at screening and at follow-up visits if nitrites or leukocyte esterase is detected by dipstick; however, urine culture is not required.

^d Questionnaires will be collected in a paper format.

^e An existing cystoscopy evaluation can be used if performed within 6 months prior to the time of consent.

^f If the biopsy procedure is scheduled more than 30 days after the most recent bloodborne pathogen tests were completed, the bloodborne pathogen tests (i.e. hepatitis B, hepatitis C, HIV, and syphilis) must be repeated before the biopsy procedure to confirm the patient's continued eligibility for study participation.

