7.8.3 Follow-up (Visit 4) – Treatment Month 1 (\pm 1 week)

A clinical assessment will be performed. Patients will provide a completed 24-hour pad test, and will have a urine sample collected to test for nitrites and leukocyte esterase. If the urine test is positive for nitrites or leukocyte esterase, then it is recommended a urine culture be performed. Blood samples will be collected to assess PSA levels, hematocrit, hemoglobin, WBC count, BUN or urea, and creatinine. PVR urine volume will also be determined via ultrasound/bladder scan. If, after multiple void attempts, the PVR volume is \geq 200 mL, additional evaluation for obstruction is recommended. During the visit, patients will complete the following questionnaires: ICIQ, IQOL, PGI-S, I-PSS, IIEF-5, and PGI-I. The medication log will be updated if necessary. Any adverse events occurring since the last contact will be recorded and reported as appropriate.

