7.8.5 Follow-up (Visit 6) – Treatment Month 6 (- 2, + 4 weeks)

A clinical assessment will be performed. Patients will provide a completed 24-hour pad test, and will have a urine sample collected to test for nitrites and leukocyte esterase. If the urine test is positive for nitrites or leukocyte esterase, then it is recommended a urine culture be performed. PVR urine volume will also be determined via ultrasound/bladder scan. If, after multiple void attempts, the PVR volume is ≥ 200 mL, additional evaluation for obstruction is recommended. During the visit, patients will complete the following questionnaires: ICIQ, IQOL, PGI-S, I-PSS, IIEF-5, and PGI-I. The medication log will be updated if necessary. Any adverse events occurring since the last visit will be recorded and reported as appropriate.

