8.3 General Analysis

Statistical analyses will be performed using SAS[®] for Windows[®] (release 9.3 or higher) or other widely accepted statistical software. Continuous variables will be reported as means and standard deviations unless otherwise noted. Categorical variables will be reported as percents. Ninety-five percent (95%) confidence intervals for all endpoint variables will be presented. Survival analysis techniques such as Kaplan-Meier or Cox Proportional Hazards may be incorporated if censoring of data occurs.

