APPENDIX E

Definitions

Definitions for the following terms are not provided in this CIP, but can be found in the applicable regulations and guidances:

Adverse Events

Adverse Drug Reaction

Life-threatening Adverse Event or Life-threatening Suspected Adverse Reaction

Serious Adverse Event or Serious Suspected Adverse Reaction

Serious Adverse Drug Reaction

Serious and Unexpected Suspected Adverse Reaction

Suspected Adverse Reaction

Unexpected Adverse Event or Unexpected Suspected Adverse Reaction

Unexpected Adverse Drug Reaction

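### The stated summary for the primary safety endpoint PVR (mean, SD, 95% CI) cannot show how many patients reach the plan's own 200 mL follow-up level; adding a count is a cheap, minor improvement

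*Combined protocol and SAP*

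**What the plan says.** Section 6.3.1 lists three primary safety endpoints. Two concern adverse events. The third stands apart from them: "PVR urine volume reported through 12-month follow-up". It is a volume, with no category or cut-off attached.

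Section 6.3.3 gives the reason for measuring it: "PVR volume will be assessed throughout the study to monitor potential retention or obstruction". Section 6.4 states the measurement and its times: "Ultrasound/bladder scan determination of PVR volume on the day of injection and at 1, 3, 6 and 12 months post-treatment".

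The analysis rule is in section 8.3 and does not name PVR: "Continuous variables will be reported as means and standard deviations unless otherwise noted". The same section adds that 95% "confidence intervals for all endpoint variables will be presented". Categorical variables are to be given as percents, and survival methods may be used if data are censored, but no PVR category or PVR event is defined for either rule to act on. No section notes a different summary for PVR.

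Sections 7.8.3 to 7.8.6 (Months 1, 3, 6 and 12) each say what follows when PVR stays high after multiple void attempts, at or above "200 mL, additional evaluation for obstruction is recommended". That is the only use made of the level. Section 7.7, which covers the Day 0 reading taken after injection, does not mention it.

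**The concern.** Retention and obstruction are patient-level findings. In at most 30 men, the safety question is whether anyone, and how many, had a markedly raised residual. A mean averages a few high readings with many low ones, and its CI describes the average man.

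If the plan is followed exactly as written, the final report could meet its PVR commitment without saying how many treated men reached the level at which the plan itself recommends looking for obstruction. In a small descriptive safety study with no test and no power calculation, the summaries are the result, so the choice of summary matters.

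**Working it through.** The plan gives no figure to reproduce: sections 8.1 and 8.2 state no power and no sample size calculation, and no PVR distribution appears anywhere. The check is therefore whether the stated summary determines the count.

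**Inputs.** From the documents: n = 30 (the maximum, section 8.2); level 200 mL (sections 7.8.3 to 7.8.6); mean, SD and 95% CI (section 8.3). Assumed: the PVR values themselves, and a t-based CI, since the plan names no method.

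**Two assumed sets of 30 readings (mL).**

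- Set A: 199, 199, 197, 197, 189, 96, 79, 74, 74, 46, 19, 14, 7, 7, 7, 7, 5, 5, 4, 4, 3, 2, 2, 1, 1, 1, 1, 0, 0, 0
- Set B: 213, 206, 204, 202, 200, 57, 46, 38, 29, 26, 24, 23, 23, 19, 15, 13, 13, 12, 11, 11, 10, 10, 8, 6, 6, 4, 3, 3, 3, 2

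**Summary under section 8.3.** Mean = sum/30. SD = √(SS/29), where SS is the sum of squared deviations from the mean. CI = mean ± 2.045 × SD/√30.

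| | Set A | Set B |
|---|---|---|
| Sum | 1440 | 1440 |
| Mean | 48.0 | 48.0 |
| SS | 152,802 | 152,758 |
| SD | 72.6 | 72.6 |
| 95% CI | 20.9 to 75.1 | 20.9 to 75.1 |
| Patients at or above 200 mL | 0 | 5 |
| Median | 7 | 14 |
| Maximum | 199 | 213 |

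To the precision a report would print, the stated summary is identical and the counts are 0 and 5. The CI cannot separate the sets, because it depends only on mean, SD and n.

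**Limit of the ambiguity in this example.** The smallest SS with k patients at or above 200 mL puts those k at exactly 200 and the rest at one common value.

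- k = 5: the other 25 average (1440 − 1000)/25 = 17.6. SS = 5 × 152² + 25 × 30.4² = 115,520 + 23,104 = 138,624. This is below about 152,800, so 5 is possible.
- k = 6: the other 24 average (1440 − 1200)/24 = 10. SS = 6 × 152² + 24 × 38² = 138,624 + 34,656 = 173,280. This exceeds about 152,800, so 6 is impossible.

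This mean and SD therefore cannot go with more than 5 patients, and the two sets show that both 0 and 5 occur.

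**A second example.** Three patients at 250 mL and 27 at 20 mL give mean 43.0, SD 70.2 and CI 16.8 to 69.2 mL. Six at about 181.0 mL and 24 at about 8.5 mL give the same three figures. The counts are 3 and 0.

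**What a count would give.** Exact (Clopper-Pearson) 95% CIs, where for zero events the upper limit is 1 − 0.025^(1/n):

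- 0/30: 0 to 11.6%
- 1/30 = 3.3%: 0.1 to 17.2%
- 3/30 = 10.0%: 2.1 to 26.5%
- With fewer treated: 0/20 gives 0 to 16.8%, and 0/10 gives 0 to 30.8%

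**The case against.** The strongest reply is that this is a preference about tables. The study is preliminary, single-arm and unpowered. Section 8.3 sets a general default, allows exceptions and does not bar further tables. Section 6.3.1 defines the endpoint as a volume, and the 200 mL level is a prompt for clinical evaluation that the plan never offers as an analysis category. All of this is true. It means the plan is incomplete rather than contradictory, and it caps the point at minor. It does not remove the gap, because nothing commits the sponsor to the count.

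A second reply is that adverse event reporting already covers these men. Events are collected at every contact, and section 12.0 has each assessed for relationship, severity, intervention and resolution. A man evaluated for obstruction could well appear there. This stands in part. However, no section makes a PVR at this level an event, and Appendix E leaves the terms to outside sources: "Definitions for the following terms are not provided in this CIP, but can be found in the applicable regulations and guidances". In addition, the non-serious event endpoint in section 6.3.1 counts only events related to product, biopsy or injection. A raised PVR without symptoms could fall outside it.

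A reader might infer that raised residuals will go unreported, or that the trial's safety assessment fails. The documents do not support that: PVR is measured at every office visit after treatment, further evaluation is recommended, and the sponsor remains free to tabulate counts. A reader might also infer that 200 mL is a failed endpoint criterion; it is not an endpoint criterion at all.

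The example sets are constructed, and Set A has four values just under the level. They prove that the summary does not fix the count; they do not predict what this trial will see.

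**Conclusion.** The point holds as a minor improvement to a descriptive report. The only stated summary for a primary safety endpoint does not answer the question the plan gives for measuring it. In the worked example the same mean, SD and CI go with 0 or 5 of 30 patients at or above 200 mL. No stated figure is wrong, and no test, error rate or sample size is affected.

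The size of the ambiguity rests on assumed PVR values, n = 30 and a t-based CI. The logical point, that mean, SD and n do not determine the count, rests on none of these values in particular. That no PVR count, median or maximum is planned rests on the text of sections 6.3, 6.4, 7.8 and 8.3 as published.

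**What to change.** In section 8.3, with a cross-reference in section 6.4, add for PVR:

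- **Each visit.** The number and percent of patients at or above 200 mL after repeat voids at each of Months 1, 3, 6 and 12, out of patients with a reading at that visit, with exact 95% CIs.
- **Any visit.** The number and percent reaching the level at any of these visits, out of treated patients with at least one Month 1 to 12 reading, with an exact 95% CI. Beside it, show the same figure among patients who either reached the level or had all four readings. Participation can end early (section 7.11), and this keeps missed visits from being counted silently as non-events.
- **Unrepeated readings.** List separately any reading at or above 200 mL with no recorded repeat void.
- **Distribution.** Give the median and maximum beside mean and SD at every visit. The maximum shows whether anyone reached the level; only the count shows how many.

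State that the 200 mL level is used for reporting only and changes no clinical rule.

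The cost is a few lines of text, one extra table and possibly one data field for repeat voids; the case report forms are not in the documents, so they may already record this. No new measurement is needed. With 30 or fewer patients the intervals are wide (0/30 still allows up to 11.6%), so the count is descriptive and cannot establish that retention is rare.
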